10.0 CRITERIA FOR EVALUATION AND ENDPOINT DEFINITIONS

10.1 Disease Status Criteria:

NOTE that the kinds of cells considered equivalent to blasts and included in the calculation of blast percentages depend on the FAB classification (see Section [4.1a.2](#))

a. Bone Marrow:

A1. Maturation of all cell lines; and < 5% blasts; and no Auer rods.

A2. Same as A1, except blasts \geq 5% and < 25%.

A3. Failure to meet the criteria for A1 or A2.

b. Peripheral Blood:

B1. Neutrophils > 1,000/mcl; and platelets > 100,000/mcl; and no leukemia blasts in the peripheral blood.

B2. Failure to meet the criteria for B1.

c. Extramedullary Disease:

C1. None

C2. Any

10.2 Complete Remission (CR)

Attainment of A1 marrow status and B1 peripheral blood status and C1 extramedullary disease status.

10.3 Molecular Remission (MCR)

Attainment of CR with no evidence of the PML-RAR alpha transcript as measured by PCR.

10.4 Partial Remission (PR)

Attainment of A2 marrow status and B1 peripheral and C1 extramedullary disease status.

10.5 Treatment Failures

Patients who fail to achieve CR or PR following induction will be classified according to the type of failure:

a. Resistant Disease: patient survives > 30 days following completion of initial treatment course and has persistent leukemia in the most recent peripheral blood smear or bone marrow after completion of therapy.

b. Not Assessable: patient survives > 30 days following completion of initial treatment course then dies with no persistent leukemia in the peripheral smear but no post-induction bone marrow examination.

c. Treatment Failure Due to Death:

1. patient survives < 30 days after completion of initial treatment course with evidence of persistent leukemia in the peripheral smear and post induction bone marrow examination.
2. patient survives < 30 days following completion of initial treatment course then dies without determination of response.

10.6 Relapse from CR

Reappearance of leukemic blasts in the peripheral blood; or > 5% blasts in the bone marrow not attributable to another cause (e.g., recovery of normal cells following chemotherapy-induced aplasia); or appearance or reappearance of extramedullary disease or reappearance of PML-RAR alpha (in patients who had achieved MCR) via cytogenetics, FISH, or PCR in the blood or bone marrow, confirmed at least once 4 - 8 weeks later. If there are no circulating blasts and no extramedullary disease and the bone marrow blast percentage is > 5% but ≤ 20%, then a repeat bone marrow performed at least 7 days after the first marrow examination and documenting bone marrow blast percentage is > 5% is necessary to establish relapse.

10.7 Event-free survival (EFS) at 3 years

For this study, EFS at 3 years is defined as a binary variable as follows: Yes if the patient achieves CR (Section [10.2](#)) and remains in continuous CR until at least 3 years after entering the study; otherwise No.

10.8 Toxicity Criteria

The NCI Common Terminology Criteria for Adverse Events Version 3.0 will be used to determine severity of toxicity.

10.9 Performance Status

Patients will be graded according to the Zubrod performance status scale.

POINT	DESCRIPTION
0	Fully active, able to carry on all pre-disease performance without restriction.
1	Restricted in physically strenuous activity but ambulatory and able to carry out work of a light or sedentary nature, e.g., light housework, office work.
2	Ambulatory and capable of self-care but unable to carry out any work activities; up and about more than 50% of waking hours.
3	Capable of limited self-care, confined to bed or chair more than 50% of waking hours.
4	Completely disabled; cannot carry on any self-care; totally confined to bed or chair.

10.10 Time to Death

From date of registration until date of death from any cause.

11.0 STATISTICAL CONSIDERATIONS

11.1 Primary Objective

The primary objective of this study is to test whether the regimen incorporating ATRA, arsenic trioxide, and gemtuzumab ozogamicin is sufficiently safe and effective among patients with previously untreated high-risk acute promyelocytic leukemia to warrant Phase III study. This objective will be met by analyzing the probabilities of continuous complete remission (CCR) at 3 years and of death from any cause within the first 6 weeks of protocol treatment. If the 3-year CCR rate is sufficiently high AND the 6-week mortality rate is sufficiently low, then Phase III study might be warranted; otherwise further study would not be recommended. To define a test criterion based on both outcomes, it is necessary to define null and alternative hypotheses in terms of the joint distribution of efficacy and toxicity.

The regimen would not warrant Phase III study if its true 3-year CCR rate is 50% or less OR its 6-week mortality rate is 30% or more. Therefore, the joint distribution of the null hypothesis with marginal probabilities is the following:

CLOSED EFFECTIVE 06/01/2013

Null Hypothesis Joint Distribution:

Death within first 6 weeks	Died or relapsed within 3 years, or no CR	Alive in CR at 3 years
Yes	30%	0%
No	20%	50%

The regimen would warrant Phase III study if its true 3-year CCR rate is 70% or higher AND its true fatal toxicity rate is 15% or less. Therefore, the joint distribution of the alternative hypothesis with marginal probabilities is the following:

Alternative Hypothesis Joint Distribution:

Death within first 6 weeks	Died or relapsed within 3 years, or no CR	Alive in CR at 3 years
Yes	15%	0%
No	15%	70%

Because there is only limited Group-wide experience with this regimen, accrual will be conducted in two steps. In the first step, 32 eligible patients will be accrued. If more than seven of these patients die within the first 6 weeks, then the study will be terminated early with the conclusion that the study does not warrant Phase III study. Otherwise an additional 38 eligible patients will be accrued. Patients enrolled before RT-PCR results are known and who are subsequently found to be negative for PML-RAR α and RAR α -PML will not be counted towards these accrual goals.

If, among the total of 70 eligible patients, at least 41 are alive and in continuous CR at 3 years and fewer than 17 die in the first 6 weeks, then Phase III study will be warranted. For the null hypothesis joint distribution above, the probability of early stopping is 0.79, and the critical level (the probability of erroneously concluding that the regimen warrants Phase III study) of the study is 0.033. For the joint distribution of the alternative hypothesis, the probability of early stopping is 0.096, and the power (the probability of correctly concluding that Phase III study is warranted) is 0.89. The statistical characteristics are summarized in the following table:

Hypothesis	Null	Alternative
Probability of 8+ deaths within 6 weeks in first 32 patients	0.79	0.096
Probability of 41+ CCR at 3 yrs and < 17 deaths within 6 weeks in 70 patients	0.033	0.89

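### The critical level of 0.033 holds only where both rates sit at their null limits; over the OR-type null that Section 11.1 defines, the false-go probability reaches 0.094

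*Combined protocol and SAP*

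**What the plan says.** All of this is in Section 11.1 (Primary Objective) of the combined protocol and SAP.

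- **Null region.** The regimen is not worth a Phase III study if its "true 3-year CCR rate is 50% or less OR its 6-week mortality rate is 30% or more".
- **Null point.** The next sentence begins "Therefore, the joint distribution of the null hypothesis with marginal probabilities is the following". It leads to one table: 30% early death, 20% later failure or no CR, 50% alive in CR at 3 years.
- **Alternative.** The regimen is worth a Phase III study if its "true 3-year CCR rate is 70% or higher AND its true fatal toxicity rate is 15% or less". The tabulated point is 15% / 15% / 70%.
- **Stage 1.** The first stage enrols 32 eligible patients. The stopping rule reads "If more than seven of these patients die within the first 6 weeks, then the study will be terminated early".
- **Stage 2.** "Otherwise an additional 38 eligible patients will be accrued", for a total of 70. Phase III study is warranted if "at least 41 are alive and in continuous CR at 3 years and fewer than 17 die in the first 6 weeks".
- **Stated properties.** At the tabulated null point, early stopping is put at 0.79, and the text adds that the "critical level (the probability of erroneously concluding that the regimen warrants Phase III study) of the study is 0.033". At the alternative point, early stopping is 0.096 and power is 0.89. The summary table repeats these figures under columns headed Null and Alternative.

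No error rate is given for any other point of the null, and no target or maximum type I error is stated.

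**The concern.** The null is a union: either bad rate alone is enough to make a go decision wrong. A single point where both rates are bad does not follow from that statement, although the text presents it as a consequence.

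The choice of point matters because the go rule is an intersection. At the joint point a false go must get past two criteria that both work against it. If only one rate is bad, the other criterion passes easily and gives little protection. Along the boundary of the null, the joint point is therefore where the error is lowest.

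Two wrong decisions are at stake: advancing a regimen that is safe early on but no better than 50% CCR, and advancing one with good CCR but 30% early mortality. The two criteria exist to prevent exactly these. A reader who takes 0.033 as the risk of an erroneous go under the stated null would underestimate both.

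**Working it through.** **Inputs (Section 11.1).** 32 + 38 = 70 patients; stop if early deaths in stage 1 are 8 or more; go if total early deaths are 16 or fewer and CCRs are 41 or more. Let pD be the 6-week death rate and pC the 3-year CCR rate. As in the protocol's tables, a patient who dies early cannot be in CCR. Patients are taken as independent.

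**Formula.** With d1 early deaths in stage 1, d2 in stage 2, and d = d1 + d2:

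P(go) = Σ over d1 ≤ 7, d ≤ 16 of P[Bin(32, pD) = d1] × P[Bin(38, pD) = d2] × P[Bin(70 − d, pC/(1 − pD)) ≥ 41]

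**Step 1: reproduce the stated figures.**

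| Quantity | Stated | Recomputed |
|---|---|---|
| P[Bin(32, 0.30) ≥ 8] | 0.79 | 0.788 |
| P[Bin(32, 0.15) ≥ 8] | 0.096 | 0.0958 |
| P(go) at pD = 0.30, pC = 0.50 | 0.033 | 0.0326 |
| P(go) at pD = 0.15, pC = 0.70 | 0.89 | 0.887 |

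All four agree, so this is the protocol's own model and rounding is not the issue. A simulation with 2,000,000 draws per scenario gave 0.0327 and 0.887 for the last two rows.

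**Step 2: move along the CCR boundary (pC = 0.50).**

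| Early mortality | False-go probability |
|---|---|
| 30% | 0.0326 |
| 25% | 0.0630 |
| 20% | 0.0834 |
| 15% | 0.0919 |
| 10% | 0.0939 |
| 5% | 0.0941 |
| 0% | 0.0941 |

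**Step 3: move along the mortality boundary (pD = 0.30).**

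| CCR | False-go probability |
|---|---|
| 50% | 0.0326 |
| 55% | 0.0657 |
| 60% | 0.0783 |
| 65% | 0.0790 |
| 70% | 0.0790 |

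**Step 4: the maximum over the whole null.** Each part of the union has a simple bound.

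- If pC ≤ 0.50, a go requires at least 41 CCRs, so P(go) ≤ P[Bin(70, 0.50) ≥ 41] = 0.0941. This is attained as early mortality goes to zero.
- If pD ≥ 0.30, a go requires d1 ≤ 7 and d ≤ 16, so P(go) is at most the probability of that event at pD = 0.30, which is 0.0790.

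The maximum over the union is the larger of the two, 0.0941. A search on a 0.01 grid over the null region gave the same value. Ratio to the stated level: 0.0941 / 0.033 = 2.85.

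**The case against.** The strongest reply is that the condition is disclosed. The sentence giving 0.033 opens by tying it to the joint distribution just tabulated, and the section says beforehand that the hypotheses will be defined through a joint distribution. Read that way, 0.033 is correct. This stands as far as it goes: there is no computational slip. But the same sentence calls the figure the critical level of the study and explains it as the probability of wrongly concluding that Phase III is warranted. Under the section's own OR statement, that conclusion is wrong across the whole union.

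Second, no ceiling on the error rate is declared, so 0.094 breaches nothing, and a one-sided error of that size does not by itself invalidate a single-arm Phase II rule. This also stands. The point concerns the reported figure, not the acceptability of the rule.

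Third, the maximum needs unusually low early mortality. Section 2.0 cites early death of at least 20% in high-risk patients, and 24% in one trial; at CCR 50% these give 0.083 and 0.068. On the mortality boundary, CCR of 60% to 70% means that 60/70 = 86% to 70/70 = 100% of six-week survivors are in CCR at 3 years. If 24% of survivors failed later, taking the recurrence rate of another cited trial as a stand-in, CCR would be 0.70 × 0.76 = 53% and the false-go probability about 0.055. So 2.85 times is an upper bound. All these values still exceed 0.033, and 15% mortality with 50% CCR, which uses the protocol's own alternative mortality, gives 0.092.

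**Conclusion.** The concern holds. The value 0.033 is right at the single point where it was computed, but it is not the critical level for the null that Section 11.1 defines. Over that null the false-go probability reaches 0.094 on the CCR boundary and 0.079 on the mortality boundary. At the more ordinary values examined (early mortality of 20% to 25% with CCR of 50%) it is 0.063 to 0.083, about two to two and a half times the stated figure.

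The result rests on the protocol's own sample sizes and cut-offs, on independent patients, and on early death excluding CCR. It needs no outside figure. The stopping rule, go rule, sample size and power at the stated alternative are unaffected.

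**What to change.** Restate the critical level in Section 11.1 and in its summary table, for example: the probability of a false go is 0.033 when both rates are at their null values; its maximum over the null hypothesis (CCR at or below 50%, or 6-week mortality at or above 30%) is 0.094, reached on the CCR boundary; the maximum on the mortality boundary is 0.079. The sentence that moves from the OR condition to the single table should say that the table is one chosen point of the null, not a consequence of it.

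The cost is a sentence and a table entry, and a less favourable stated error rate. No patients, data or cut-offs change. The trial passed its first stage (Revision #7 notice) and is marked closed effective 06/01/2013, so the correction should also carry into any report that quotes the critical level.

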11.2 Molecular Response and Toxicity

With 70 eligible patients, the probabilities of molecular response and of any particular toxicity can be estimated to within at most $\pm 12\%$ (95% confidence interval). Any toxicity occurring with at least 5% probability is very likely to be observed in at least one patient (probability $\geq 97\%$).

11.3 Accrual

The recent intergroup APL study **C9710**, accrued about 25 eligible high-risk patients per year. Therefore accrual of 70 eligible patients to this study is expected to require approximately 34 months assuming there is not a lengthy delay between the two stages of accrual.

11.4 Data Safety Monitoring

There is no formal data and safety monitoring committee for Phase II studies. Toxicity and accrual monitoring are done routinely by the Study Chair, study Statistician and the Disease Committee Chair. Response monitoring is done by the study Statistician and Study Chair. Accrual reports are generated weekly, and formal toxicity reports are generated every 6 months. In addition, the Statistical Center, Adverse Event Coordinator at the Operations Office, and Executive Officer monitor toxicities on an ongoing basis.

12.0 DISCIPLINE REVIEW

Discipline review is not necessary for this study.

13.0 REGISTRATION GUIDELINES

NOTE: For non-SWOG member procedures (CTSU participation) see Appendix [18.4](#).

13.1 Registration Timing

Patients must be registered prior to initiation of Induction (Step 1—Initial Registration), Consolidation (Step 2—Consolidation Therapy Registration), or Maintenance (Step 3—Maintenance Therapy Registration) treatment no more than one working day prior to planned start of treatment.

13.2 Registration Requirements

For either phone or web registration, the individual registering the patient must have completed the appropriate Southwest Oncology Group Registration Form. The completed form must be referred to during the registration but should not be submitted as part of the patient data.

The individual registering the patient must also be prepared to provide the treating institution's name and ID number in order to ensure that the current (within 365 days) date of institutional review board approval for this study has been entered into the data base. Patients will not be registered if the IRB approval date has not been provided or is > 365 days prior to the date of registration.

13.3 Registration Procedures

- a. You may register patients from Member, CCOP and approved Affiliate institutions to a therapeutics study using the SWOG Registration program. To access the Registration program go to the SWOG Web site (<http://swog.org>) and click on the Logon link to go to the SWOG Members Area logon page (<https://swog.org/visitors/logon.asp>). This Web program is available at any time except for periods listed under Down Times. Log on as an Individual User using your SWOG Roster ID Number and individual web user password. Help for the logon process may be found at <https://swog.org/visitors/logonhelp.asp>. After you have logged on, click on the Clinical Trials link and then the Patient Reg link to go

to the Entry Page for the Patient Registration program. If you are a Registrar at an institution with Internet access you are encouraged to register this way. For new users, the link to a "Starter Kit" of help files may be found by clicking on Starter Kit link at the logon page.

To register a patient the following must be done (in order):

1. You are entered into the Southwest Oncology Group Roster and issued a SWOG Roster ID Number,
2. You are associated as an investigator or CRA/RN to the institution where a registration is occurring, and
3. You are granted permission to use the Patient Registration program at that institution.

For assistance with points 1 and 2 call the SWOG Operations Office at [name]. For point 3 you must contact your Web User Administrator. Each SWOG institution has one or more Web User Administrators who may set up Web Users at their institution and assign permissions and passwords to these users. For other password problems or problems with the Patient Registration program, please e-mail [contact]. Include your name, Roster ID Number, and telephone number, when the problem occurred, and exactly what you were doing.

- b. If the Web Reg program is not used, the registration must be done by phone.

Member, Affiliate and CCOP Institutions

Registration by phone of patients from member, affiliate and CCOP institutions must be done through the Southwest Oncology Group Data Operations Center in Seattle by telephoning [name], 6:30 a.m. to 4:00 p.m. Pacific Time, Monday through Friday, excluding holidays.

- 13.4 For either method of registration, exceptions to Southwest Oncology Group registration policies will not be permitted.
 - a. Patients must meet all eligibility requirements.
 - b. Institutions must be identified as approved for registration.
 - c. Registrations may not be cancelled.
 - d. Late registrations (after initiation of treatment) will not be accepted.

14.0 DATA SUBMISSION SCHEDULE

14.1 Data Submission Requirements

Data must be submitted according to the protocol requirements for ALL patients registered, whether or not assigned treatment is administered, including patients deemed to be ineligible. Patients for whom documentation is inadequate to determine eligibility will generally be deemed ineligible.

14.2 Master Forms

Master forms are included in [Section 18.0](#) and (with the exception of the sample consent form and the Registration Form) must be submitted to the Data Operations Center in Seattle. Data from approved SWOG institutions must be submitted on-line via the Web; see [Section 14.3a](#) for details. Exceptions to online data submission are patient-completed (e.g. Quality of Life) forms and source documents (e.g. pathology/operative/lab reports).

14.3 Data Submission Procedures

- a. Southwest Oncology Group institutions must submit data electronically via the Web by using the SWOG CRA Workbench. To access the CRA Workbench, go to the SWOG Web site (<http://swog.org>) and logon to the Members Area. After you have logged on, click on the CRA Workbench link to access the home page for CRA Workbench website. Next, click on the Data Submission link and follow the instructions. For new users, the link to a "Starter Kit" of help files may be found by clicking on the Starter Kit link at the Members' logon page.

To submit data via the web the following must be done (in order):

1. You are entered into the Southwest Oncology Group Roster and issued a SWOG Roster ID Number,
2. You are associated as an investigator or CRA/RN at the institution where the patient is being treated or followed, and
3. Your Web User Administrator has added you as a web user and has given you the appropriate system permissions to submit data for that institution.

For assistance with points 1 and 2 call the Operations Office at [name]. For point 3, contact your local Web User Administrator (refer to the "Who is my Web User Administrator?" function on the swog.org Members logon page). For other difficulties with the CRA Workbench, please email [contact].

- b. If you need to submit data that are not available for online data submission, the only alternative is via facsimile. Should the need for this occur, institutions may submit data via facsimile to [name] or [name] locally. Please do not use cover sheet for faxed data.

14.4 Data Submission Overview and Timepoints

- a. WITHIN 14 DAYS AFTER INITIAL REGISTRATION (STEP 1):

Submit the following:

S0535 Prestudy Form

Pathology Report

Pretreatment Cytogenetics Report (only required for patients from SWOG sites and other sites NOT affiliated with ECOG or CALGB)

Pretreatment RT-PCR Report (only required for patients from SWOG sites, CALGB sites and other sites NOT affiliated with ECOG)

See Section [15.0](#) for sample submission requirements.

- b. WITHIN 14 DAYS AFTER COMPLETING INDUCTION TREATMENT:

Submit the following:

S0535 Induction Treatment Summary Form

S0535 Adverse Event Summary Form

APL Disease Assessment Form

Off Treatment Notice (Please enter Step "1" on form.)

RT-PCR Report (only required for patients from SWOG sites, CALGB sites and other sites NOT affiliated with ECOG)

- c. WITHIN 14 DAYS AFTER COMPLETING EACH OF CONSOLIDATION CYCLES 1 AND 2 TREATMENT:

Submit the following:

S0535 Consolidation Cycles 1 and 2 Treatment Summary Form

S0535 Adverse Event Summary Form

- d. WITHIN 14 DAYS AFTER COMPLETING CONSOLIDATION CYCLE 2:

Submit the following:

APL Disease Assessment Form

RT-PCR Report (only required for patients from SWOG sites, CALGB sites and other sites NOT affiliated with ECOG)

- e. WITHIN 14 DAYS AFTER COMPLETING EACH OF CONSOLIDATION CYCLES 3 AND 4 TREATMENT:

Submit the following:

S0535 Consolidation Cycles 3 and 4 Treatment Summary Form

S0535 Adverse Event Summary Form

- f. WITHIN 14 DAYS AFTER COMPLETING EACH OF CONSOLIDATION CYCLES 5 AND 6 TREATMENT:

Submit the following:

S0535 Consolidation Cycles 5 and 6 Treatment Summary Form

S0535 Adverse Event Summary Form

- g. WITHIN 14 DAYS AFTER COMPLETING CONSOLIDATION CYCLE 6:

Submit the following:

APL Disease Assessment Form

- h. WITHIN 14 DAYS AFTER GOING OFF CONSOLIDATION TREATMENT:

Submit the following:

Off Treatment Notice (Please enter Step "2" on form.)

- i. WITHIN 14 DAYS AFTER REGISTRATION FOR MAINTENANCE THERAPY (Step 3):

Submit the following:

APL Disease Assessment Form

RT-PCR Report (only required for patients from SWOG sites, CALGB sites and other sites NOT affiliated with ECOG)

- j. EVERY 3 MONTHS WHILE ON MAINTENANCE THERAPY:
Submit the following:
S0535 Maintenance Treatment Summary Form
S0535 Adverse Event Summary Form
APL Disease Assessment Form
- k. WITHIN 14 DAYS AFTER GOING OFF MAINTENANCE TREATMENT:
Submit the following:
Off Treatment Notice (Please enter Step "3" on form.)
- l. WITHIN 14 DAYS AFTER KNOWLEDGE OF A RELAPSE FROM COMPLETE REMISSION:
Submit the following:
A copy of the APL Disease Assessment Form documenting the date of and evidence for complete remission or relapse.
Submit Cytogenetics Report (only required for patients from SWOG sites and other sites NOT affiliated with ECOG or CALGB)
RT-PCR Report (only required from SWOG sites, CALGB sites and other sites not affiliated with ECOG)
- m. AFTER OFF TREATMENT: THE REMAINING OF MONTHS 3, 6, 9, 12, 18, 24 AND 36 FROM THE TIME OF INITIAL REGISTRATION:
Submit the following:
Follow Up Form.
- n. WITHIN 4 WEEKS AFTER KNOWLEDGE OF DEATH:
If death occurs while patient is on protocol treatment submit a copy of the Notice of Death, the **S0535** Adverse Event Summary Form and the Treatment Summary Form that corresponds with the Step and Cycle of treatment the patient was receiving at the time of death.
If the death occurs after off treatment submit a final Southwest Oncology Group Follow Up Form. Also submit a copy of the Notice of Death.

